### **Data separation**

AI processing of participant ECG data will be undertaken on Imperial College London computers. All linked procedural data from the EP study (i.e. 3D electroanatomical mapping data, human operator prediction, procedure report and fluoroscopy frames) will be strictly separated from the AI algorithm. The AI algorithm will be applied by a researcher, blinded to the true accessory pathway location, and the resulting output will be stored separately. We will maintain strict division of data so that researchers inputting ECG data into the AI algorithms and analysing its outputs are analysed independently of the operator predictions, thus minimising any performance bias. An independent researcher will act as a monitor for the research protocol. Finally, the human operators and team performing the ablation will have no access to the outcome of the AI prediction at any point.

### **Operator workflow**

Using the patient's 12-lead ECG, the operator will be asked to make a prediction of the accessory pathway location within the case report form prior to the start of the procedure, which can be performed using their own analysis or via a manual algorithm (such as Arruda), according to their preference.

All patients will undergo their planned EP study. There will be no change to their clinical treatment. As part of the procedure, operators will be able to perform their usual procedural workflow for accessory pathway identification and ablation, whether that be using electroanatomical mapping, fluoroscopy or electrograms or a combination of these. As part of the data collection during the case, we request operators to collect the following data to determine the true accessory pathway location:

- The electroanatomical location of the final ablation lesion which resulted in loss of pathway conduction, which should be tagged.
- Sufficient electroanatomical geometry to produce a complete annular map on the side of the accessory pathway, to accurately assess the true location of the accessory pathway on the annulus
- The fluoroscopy image demonstrating the catheter position on pathway ablation.

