**GLOSSARY OF ABBREVIATION**

AI	Artificial intelligence
ECG	Electrocardiogram
EPS	Electrophysiology study
PPG	Photoplethysmography
HCP	Healthcare professional

STUDY SUMMARY

TITLE	AI-ECG Accessory Pathway Localisation Study
DESIGN	Prospective validation study
AIMS	
 
1) To develop and finalise a machine learning algorithm to localise accessory pathways from the 12-lead ECG.
 
2) To prospectively validate machine learning algorithms for accessory pathway localisation through a clinical trial.
 

OUTCOME MEASURES	
 
• Key deliverable: A prospectively validated AI algorithm for accessory pathway localisation, which can produce reliable, reproducible and accurate outputs
 
• Outcome measures: 
 
• Overall accuracy of the AI algorithm predictions, as compared to the operator assessment.
 
• Overall accuracy of the AI algorithm predictions, as compared to the ground truth of successful ablation location determined by fluoroscopy <math>\pm</math> 3D mapping.
 
• Sensitivity, specificity, positive and negative predictive values, and F1 score of the ECG AI algorithm for accessory pathway localisation
 
• Difference in accuracy between the AI algorithm prediction and human estimation from the 12-lead ECG.
 
• Difference in accuracy between the AI algorithm and pre-specified, established manual localisation algorithms (Arruda, Milstein, Pambrun, Boersma, D'Avila and Chiang).
 
• Correlation of accessory pathway localisation by human estimation, and manual algorithm output as compared to the true location on 3D mapping.
 
 
 

POPULATION	Patients referred for an EPS
ELIGIBILITY	
Inclusion Criteria
 
 
1) Age 13 - 100 years old
 
2) Referred for invasive electrophysiological study as part of their usual clinical care
 
3) Manifest pre-excitation on their ECG any time prior to their procedure
 
4) Able to give consent
 
 
Exclusion criteria
 
 
1) Patients with known location of their accessory pathway from a previous EPS
 
2) Age <math><13</math> years old
 
3) Age <math>> 100</math> years old
 

DURATION	1 st March 2025 – 1 st March 2027

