## 1. INTRODUCTION

### 1.1 BACKGROUND

Accessory pathways are congenital cardiac abnormalities that can enable electrical impulses to bypass normal atrioventricular nodal conduction. This leaves patients at risk of supraventricular tachycardias and even sudden death in the case of pre-excited atrial fibrillation. The location of an accessory pathway can be definitively established by successful ablation. It is desirable to localise a suspected accessory pathway prior to an invasive electrophysiological study both to guide procedure planning and to personalise the consent process: pathway location determines much of individual procedure risk.

Accessory pathway location can be estimated from the 12-lead ECG using either human expertise or manual localisation algorithms that rely on specific ECG features. These approaches are subject to inter-operator variability and are often time consuming and difficult to perform for inexperienced users, respectively. Validation studies of these algorithms have not shown high accuracy, or even reproducibility in some cases. These studies are also problematic due to being either retrospective, using strict eligibility criteria not representative of clinical practice, or validation cases being entirely non-external.

Artificial intelligence has been increasingly investigated for its role as a high-performance predictive tool in healthcare and beyond. Machine learning algorithms can reproducibly classify medical data with very high levels of accuracy. Within cardiology, AI has been successfully applied to ECG interpretation for several cardiac conditions. Our group has developed a proof-of-concept AI algorithm for accessory pathway localisation, which has demonstrated an accuracy of 93% when retrospectively applied to 156 12-lead ECGs (left vs septal vs right).

To formally validate the real-world accuracy of this AI algorithm for accessory pathway localisation, it is imperative that: 1. The algorithm is tested **prospectively**; 2. The algorithm is tested on **consecutive** cases, avoiding cherry-picking; 3. The tested algorithm is locked such that it cannot be influenced by any new data during testing. 4. The testing cohort must include **external** cases, to avoid AI overfitting and test generalisability. These standards are essential for robust validation and to provide a genuine assessment of the accuracy for the algorithm before real-world application and use in clinical practice.

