### Secondary objectives

- 1) To evaluate the relative performance of the AI algorithm compared to human interpretation and conventional manual algorithms.
- 2) To compare the accuracy of ground truth locations to complete annular maps from 3D electro-anatomical mapping.

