#### **Secondary Outcome Measures**

- Sensitivity, specificity, positive and negative predictive values, and F1 score of the ECG AI algorithm for accessory pathway localisation.
- Difference in accuracy between the AI algorithm prediction and human estimation from the 12-lead ECG.
- Difference in accuracy between the AI algorithm and pre-specified, established manual localisation algorithms (Arruda, Milstein, Pambrun, Boersma, D'Avila and Chiang).
- Overall accuracy of the AI algorithm predictions, as compared to the ground truth of successful ablation location determined by fluoroscopy  $\pm$  3D mapping.
- Correlation of accessory pathway localisation by human estimation, and manual algorithm output as compared to the true location on 3D mapping

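### The one operator prediction may be made with or without a manual algorithm, so human estimation may mix the two unless the method is recorded

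*Protocol*

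**What the plan says.** Section 3.2 of the protocol, under Operator workflow, asks the operator to enter a prediction from the 12-lead ECG in the case report form before the procedure starts, "which can be performed using their own analysis or via a manual algorithm (such as Arruda), according to their preference". Under Data separation, the linked procedural data kept away from the AI are listed as "3D electroanatomical mapping data, human operator prediction, procedure report and fluoroscopy frames". The operator prediction is the only human ECG reading in that list, and the protocol describes no other.

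Elsewhere the protocol keeps human reading and manual algorithms apart:

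- Section 1.1 says: "Accessory pathway location can be estimated from the 12-lead ECG using either human expertise or manual localisation algorithms that rely on specific ECG features". It gives each its own weakness: "These approaches are subject to inter-operator variability and are often time consuming and difficult to perform for inexperienced users, respectively".
- The first secondary objective in section 2 is: "To evaluate the relative performance of the AI algorithm compared to human interpretation and conventional manual algorithms".
- The outcome measures in the Study Summary, repeated in section 3.4, include "Difference in accuracy between the AI algorithm prediction and human estimation from the 12-lead ECG" and, as a separate item, "Difference in accuracy between the AI algorithm and pre-specified, established manual localisation algorithms". Six algorithms are named, and the one given as an example under Operator workflow is among them.
- A further secondary outcome again names both: "Correlation of accessory pathway localisation by human estimation, and manual algorithm output as compared to the true location on 3D mapping".

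**The concern.** The objectives and outcomes treat human reading and manual algorithms as two comparators, but the data-collection rule lets the only described human reading be either one. An operator who applies one of the six listed algorithms would supply a human estimation that is largely the output of another comparator.

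Two secondary results are at stake: AI against human estimation, and human estimation against the 3D-mapped location. A reader would be likely to take the first as AI against unaided expert reading, when it may be AI against whatever each operator chose to do.

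This is a matter of data capture. If the method is not recorded at the time, an analysis plan cannot recover it. Agreement between an operator's prediction and an algorithm's output does not show that the algorithm was used. The operator's own unaided reading before the procedure cannot be collected once the ablation site is known, and later readings of stored ECGs by other people would be a different comparison.

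**Working it through.** **No plan figure to reproduce.** The protocol gives no accuracy for human estimation and no expected share of algorithm use. Its sample-size statement contrasts AI at 93% with the next best manual algorithm at 77%; no human rate enters it.

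**Step 1: link the passages.** Operator workflow describes one prediction. Data separation calls it a human operator prediction. Section 3.4 needs a human estimation from the 12-lead ECG, and nothing else in the protocol could supply it. The link is a strong inference, but no sentence states it.

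**Step 2: write down the effect of mixing.** Let

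- A = AI accuracy over all cases
- f = share of predictions made with an algorithm
- h0 = accuracy of the unaided predictions, in the cases read unaided
- a1 = accuracy of the aided predictions, in the cases read with an algorithm
- h1 = accuracy those same aided cases would have had if read unaided

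Measured human accuracy = (1 − f)·h0 + f·a1.

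Human accuracy had all been unaided = (1 − f)·h0 + f·h1.

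Shift in the AI-human gap = [A − measured] − [A − all unaided] = **f·(h1 − a1)**.

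A cancels. The protocol gives none of f, h1 or a1. The gap widens if h1 > a1, narrows if h1 < a1, and does not move if f = 0 or h1 = a1.

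**Step 3: scale, for an assumed 10-point difference between h1 and a1.**

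| Aided share f | Shift in AI-human gap (points, either direction) |
|---|---|
| 5% | 0.05 × 10 = 0.5 |
| 25% | 2.5 |
| 50% | 5 |
| 75% | 7.5 |
| 100% | 10 |

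**Step 4: direction.** Assume AI accuracy 93% and aided accuracy 77% (the protocol's retrospective figure for the next best manual algorithm, borrowed here), with method choice unrelated to the case or the operator.

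| Assumed unaided accuracy | Gap at f = 0 | Gap at f = 50% | Gap at f = 100% |
|---|---|---|---|
| 65% | 28 | 93 − 71 = 22 | 16 |
| 77% | 16 | 16 | 16 |
| 85% | 8 | 93 − 81 = 12 | 16 |

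Mixing can flatter the AI, penalise it, or do neither.

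**Step 5: why observed accuracies would not settle it.** The simpler form f·(h0 − a1) replaces h1 by h0. That is correct only if the choice of method is unrelated to case difficulty and operator skill, and the protocol leaves the choice to preference. For example, let both observed accuracies be 80% and f = 50%, but suppose the aided cases would have been read at 70% unaided. The simpler form gives 0.5 × (80 − 80) = 0. The true shift is 0.5 × (70 − 80) = −5 points.

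**Step 6: what a method field alone would leave.** Of the 100 planned patients, 100 × (1 − f) would have an unaided reading: 95 at f = 5%, 75 at 25%, 50 at 50%. These would be the cases where the operator chose not to use an algorithm. I attach no interval width: the listed outcome is a within-patient difference, and its precision depends on the AI-human discordance, which the protocol does not give.

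**The case against.** The strongest reply is that usual practice is the intended comparator. No sentence says that human estimation means unaided. Section 1.1 is background and does not define an outcome. Operator workflow, the only operational text, leaves the method to the operator, which fits the aim of testing real-world accuracy with an unchanged workflow. This stands as a possible reading. It does not remove the point: the protocol never states that reading, and its objectives and outcomes name the two comparators separately.

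The case report form is also unseen and may already have a method field. A reader might infer that the method goes unrecorded; the protocol supports only that it states no such requirement. Which readings count as human estimation could be settled in an analysis plan, but only if the method had been captured.

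Three stronger readings are tempting and not supported:

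- *That the AI-human result is invalid once any operator uses an algorithm.* It remains a fair comparison with what operators did, and at a small aided share the shift is small: 0.5 points at 5% under the assumption in Step 3.
- *That mixing favours the AI.* Step 4 shows that the direction is open.
- *That the primary outcome or the AI-versus-manual comparison is contaminated.* Section 3.2 (AI algorithm testing) bases the primary outcome on the ablation site that the operator records during the procedure, not on the earlier ECG prediction. The manual-algorithm comparison is a separate outcome, and no human-versus-manual contrast is listed.

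**Conclusion.** The point holds as a cheap and worthwhile improvement to the secondary outcomes. If the operator prediction is the human estimation of section 3.4, the AI-versus-human and human-versus-3D-map results would describe operators' usual practice, a blend of unaided and aided readings in unknown proportion. Without a record of the method, the blend could not be separated afterwards.

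Size and direction cannot be derived from the protocol. The shift is f·(h1 − a1), and may be zero. The scale figures rest on assumed values of f and of the accuracies. The conclusion also rests on the inferred identity of prediction and human estimation, and on the unseen form not already capturing the method. The primary outcome, the AI-versus-manual comparison and the sample size are unaffected.

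**What to change.** Under Operator workflow, have the operator first record an unaided prediction on the case report form and then, if they wish, an aided prediction that names the algorithm. State which of the two is the human estimation of section 3.4, and report the other as supportive. This keeps the usual-practice comparison available alongside the unaided one.

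At minimum, record for each prediction whether an algorithm was used and which one. This is weaker, because it leaves fewer unaided readings and a self-selected set of cases (Steps 5 and 6).

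The cost is one or two form fields, unless the form already has them, one or two sentences in the protocol, and a short extra step for the operator. The procedure and patient care do not change. The downside is that a recorded unaided reading may anchor the aided one. The change helps only cases not yet done, so it is best made early in recruitment.

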### **Burdens/Risks:**

Patients will be subject to the small risk of their EPS procedure. The risk of this procedure includes a < 1% risk of bleeding / vascular injury, bleeding around the heart, heart attack and death. No additional risk will be conferred as part of this study as the patients will not require any additional instrumentation, monitoring or manoeuvres beyond usual routine clinical care.

Furthermore, ionising radiation will be used as part of the procedure through the use of fluoroscopy to site catheters in the correct location and change their position. We expect around 1 minute total fluoroscopy time. Appropriate radiation regulations will be followed.

Ionising radiation can cause cancer which manifests itself after many years or decades. The risk of developing cancer is estimated as 0.006% (Risk coefficient for adult population is  $5 \times 10^{-5}$  per mSv, HPA-CRCE-028) and the risk of the additional radiation to routine care is about 0.00015%. For comparison, the natural lifetime cancer incidence in the general population is about 50%.

### **3.4 STUDY OUTCOME MEASURES**

#### **Primary Outcome Measures**

- A prospectively validated AI algorithm for accessory pathway localisation, which can produce reliable, reproducible and accurate outputs.
- Overall accuracy of the AI algorithm predictions, as compared to the operator assessment.

#### **Secondary Outcome Measures**

- Sensitivity, specificity, positive and negative predictive values, and F1 score of the ECG AI algorithm for accessory pathway localisation.
- Difference in accuracy between the AI algorithm prediction and human estimation from the 12-lead ECG.
- Difference in accuracy between the AI algorithm and pre-specified, established manual localisation algorithms (Arruda, Milstein, Pambrun, Boersma, D'Avila and Chiang).
- Overall accuracy of the AI algorithm predictions, as compared to the ground truth of successful ablation location determined by fluoroscopy  $\pm$  3D mapping.
- Correlation of accessory pathway localisation by human estimation, and manual algorithm output as compared to the true location on 3D mapping

### **4. PARTICIPANT ENTRY**

#### **4.1 PRE-REGISTRATION EVALUATIONS**

Subjects will be recruited at the research site.

#### **4.2 INCLUSION CRITERIA**

##### **FOR STUDY A:**

1. Referred for EPS procedure as part of their clinical care, with a finding of pre-excitation on their ECG
2. Manifest pre-excitation on their ECG any time prior to their procedure
3. Able to give consent
4. Minimum age 13 years old
5. Maximum age 100 years old

#### **4.3 EXCLUSION CRITERIA**

- Unable to give consent
- Adults  $>$  100 years old
- Children  $<$  13 years old
- Patients with known location of their accessory pathway from a previous EP study

#### **4.4 WITHDRAWAL CRITERIA**

The research protocol will be terminated early if:

1. Patients lose their capacity to consent or become clinically unstable
2. The patient chooses to withdraw from the study
3. The sponsor, the chief investigator or the research team review the data and decide to stop the study

#### **4.5 CONSENT**

Patients will be identified by members of their direct care team when they attend clinic appointments or are admitted to the hospital. Patient records may be reviewed to assess suitability and this will be performed by members of the direct care team. Participation in the

study will be discussed with the patients by their direct care team and information will only be passed on to the research team with the patients consent. Verbal consent will be gained by the direct care team for personal contact information to be shared with the research team. This will be documented in the patient notes. The direct care team will make patients aware that participation is voluntary and that if they do not wish to participate it will not affect their usual care.

Written consent for the study will be obtained by a member of the research team, this will be a physician who is experienced in performing electrophysiology study procedures. Patients will have details of the study discussed with them and any family members or friends the patients wish to be present. They will also be provided with written information (patient information sheets). Patients will be given as much time as they wish, with a minimum of at least 24 hours, to decide whether they wish to participate in the study and will be offered additional visits to further discuss the study if they wish. Patients are able to withdraw their consent from the study at any time. Patients will be made aware that their participation is voluntary and that if they do not want to take part it will not affect their usual care. Patients who agree to take part in the study will sign a consent form, a copy of the form will be given to the patients and a second copy will be kept in their study record file. A copy will also be kept in the site file.

**Conflicts of Interest:**

There are no conflicts of interest to report.

**Dissemination of Results:**

The results will be disseminated to the scientific community through peer reviewed journal publications, internal reporting, publication on website and conference presentations. Identifiable information will not be included in the publication. Depending on patients' preferences we will either write, telephone or arrange to meet participants after the analysis has been completed. We will summarise the findings and details of how the results are relevant to them.

## 5. ADVERSE EVENTS

### 5.1 DEFINITIONS

**Adverse Event (AE):** any untoward medical occurrence in a patient or clinical study subject.

**Serious Adverse Event (SAE):** any untoward and unexpected medical occurrence or effect that:

- **Results in death**
- **Is life-threatening** – refers to an event in which the subject was at risk of death at the time of the event; it does not refer to an event which hypothetically might have caused death if it were more severe
- **Requires hospitalisation, or prolongation of existing inpatients' hospitalisation**
- **Results in persistent or significant disability or incapacity**
- **Is a congenital anomaly or birth defect**

Medical judgement should be exercised in deciding whether an AE is serious in other situations. Important AEs that are not immediately life-threatening or do not result in death or hospitalisation but may jeopardise the subject or may require intervention to prevent one of the other outcomes listed in the definition above, should also be considered serious.

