### **5.2.1 Non-serious AEs**

All such events, whether expected or not, should be recorded.

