### **5.2.2 Serious AEs**

An SAE form should be completed and emailed to the Chief Investigator within 24 hours. However, hospitalisations for elective treatment of a pre-existing condition do not need reporting as SAEs.

All SAEs should be reported to the Scotland B REC (25/SS/0034) where in the opinion of the Chief Investigator, the event was:

- ‘related’, ie resulted from the administration of any of the research procedures; and
- ‘unexpected’, ie an event that is not listed in the protocol as an expected occurrence

Reports of related and unexpected SAEs should be submitted within 15 days of the Chief Investigator becoming aware of the event, using the NRES SAE form for non-IMP studies. The Chief Investigator must also notify the Sponsor of all related and unexpected SAEs.

Local investigators should report any SAEs as required by their Local Research Ethics Committee, Sponsor and/or Research & Development Office.

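### Section 5.1 makes unexpectedness part of the SAE definition and section 5.2.2 tests it again; on one reading, fatal or immediately life-threatening listed complications miss the 24-hour form

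*Protocol*

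**What the plan says.** Section 5.1 of the protocol defines an adverse event (AE) broadly, as "any untoward medical occurrence in a patient or clinical study subject". The SAE definition adds a condition: "any untoward and unexpected medical occurrence or effect that" meets one of five criteria (death, threat to life, hospitalisation or its prolongation, disability, congenital anomaly). A closing paragraph lets medical judgement extend seriousness to "Important AEs that are not immediately life-threatening or do not result in death or hospitalisation but may jeopardise the subject", or that may need intervention to prevent a listed outcome.

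Section 5.2 asks for every AE to be reported and points to two procedures:

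- Section 5.2.1, for non-serious AEs: "All such events, whether expected or not, should be recorded". No deadline is given.
- Section 5.2.2, for SAEs: "An SAE form should be completed and emailed to the Chief Investigator within 24 hours". SAEs that the Chief Investigator considers both related and unexpected then go to the REC. Unexpected is explained there as "ie an event that is not listed in the protocol as an expected occurrence".

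Section 3.2, under Burdens/Risks, says: "The risk of this procedure includes a < 1% risk of bleeding / vascular injury, bleeding around the heart, heart attack and death".

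**The concern.** Seriousness describes the outcome of an event. Expectedness describes whether the event was foreseen. Section 5.1 merges the two, while section 5.2.2 treats them as separate steps. If every SAE is unexpected by definition, the later test removes nothing.

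What is at stake is the prompt internal report. The 24-hour form is the only timed route by which the Chief Investigator learns of an event, and section 5.2.2 asks the Chief Investigator to judge relatedness and expectedness for SAEs. An event screened out by the definition in section 5.1 never reaches that judgement. The site would have applied the expectedness test before the person named to apply it had been told.

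The gradient also runs the wrong way. Non-serious events are captured whether or not they were foreseen, while the more serious class is restricted to unforeseen ones.

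**Working it through.** No formula or stated figure is in dispute. The check is to follow an event through the definitions and routes.

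**Step 1. Is the second test redundant?** By section 5.1, SAE = untoward + unexpected + seriousness criterion. By section 5.2.2, REC report = SAE + related + unexpected. Substituting the first into the second leaves *unexpected* in the expression twice, so the second occurrence has no effect. It has an effect only if SAE = untoward + seriousness criterion. The drafting of section 5.2.2 therefore presupposes a definition that section 5.1 does not give.

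**Step 2. What counts as unexpected?** The only explanation is in section 5.2.2 and refers to what the protocol lists as expected. No list carries that title. The Burdens/Risks paragraph is the only list of foreseeable procedural complications in the text available. Two readings follow.

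| Event | Reading A: Burdens/Risks is the expected list | Reading B: it is not |
|---|---|---|
| Listed kind, fatal or immediately life-threatening | Expected, so fails the SAE definition; no 24-hour form | Unexpected, so an SAE; 24-hour form |
| Listed kind, less severe but important | Fails the main definition; may be made serious by medical judgement | SAE if a criterion is met; otherwise may be made serious by medical judgement |
| Unlisted kind, meets a seriousness criterion | SAE; 24-hour form | SAE; 24-hour form |

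Under reading B no listed event is lost, but the protocol then shows no list against which to judge expectedness, and the word still does no work in section 5.1.

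**Step 3. Does another clause catch the top-left cell?** The medical-judgement paragraph has no expectedness condition, but it is framed for situations outside the listed outcomes: "Important AEs that are not immediately life-threatening or do not result in death or hospitalisation but may jeopardise the subject". It does not by its wording reach a death. Its *or* is loose, so a threat to life that led to neither death nor hospitalisation could be argued in. The gap is clearest for fatal events.

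**Step 4. What route remains?** The event meets the AE definition, so the general instruction in section 5.2 to report all AEs applies. Of the two procedures, section 5.2.2 is closed to it. Section 5.2.1 is headed for non-serious events, which a death is not. If section 5.2.1 is used as a residual category the event is recorded, but with no deadline.

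**Step 5. How many events?** Burdens/Risks names four risks with a figure of under 1%, without saying whether that is combined or for each. With 100 patients:

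- combined: fewer than 100 × 0.01 = 1 expected event;
- each separately: fewer than 4 × 100 × 0.01 = 4 expected events, ignoring overlap.

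Only those that are fatal or immediately life-threatening fall in the gap, so these are upper limits on the expected number.

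**Step 6. Does REC reporting change?** Under reading A a listed event fails the expectedness test in section 5.2.2 whether or not section 5.1 is amended. Under reading B it is an SAE before and after. Events that reach the REC are the same either way.

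**The case against.** The strongest reply is that treating Burdens/Risks as the list of expected occurrences is an inference. Telling patients of a rare risk, including "bleeding around the heart, heart attack and death", is not plainly the same as listing death as something expected. On that view a procedural death is unexpected, meets section 5.1 and triggers the form. This stands as a limit: the loss of the 24-hour report is conditional on reading A. It does not remove the inconsistency in step 1, which holds on either reading.

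Second, section 5.2.2 itself signals that SAEs were meant to include expected events, and section 5.2 directs questions on reporting to the Chief Investigator. A sensible site might well send the form. That supports the proposed correction, but the written rule would still not describe the practice.

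Three stronger readings are tempting, and the protocol does not support them:

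- *Listed complications go unreported.* Section 5.2 still asks for all AEs to be reported. What may be lost is the SAE route and its time limit.
- *Every listed complication is affected.* Medical judgement can make less severe ones serious with no expectedness test, and that includes vascular injury or bleeding that is not immediately life-threatening.
- *The REC would be deprived of reports.* Step 6 shows that it would not.

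Finally, participants receive their planned procedure with no change in clinical treatment, and follow-up ends when it is complete, so exposure is short and events are few. That is fair, and it limits the weight of the point.

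**Conclusion.** The point holds as an internal inconsistency: sections 5.1 and 5.2.2 both use expectedness, and the second use has no function unless the first is removed. They must be reconciled.

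The practical consequence is conditional. If Burdens/Risks is taken as the list of expected occurrences, a fatal or immediately life-threatening complication of a listed kind is not an SAE as written and does not trigger the 24-hour form. It remains a reportable AE without a deadline. The number is small: on the protocol's own risk figure, fewer than one expected event in 100 patients, or fewer than four if the figure applies to each risk separately. These are, however, among the gravest events the protocol foresees. The accuracy endpoint, the analysis and the sample size are unaffected.

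**What to change.** Delete the words *and unexpected* from the SAE definition in section 5.1, so that seriousness depends on outcome alone. Keep expectedness only in section 5.2.2, as the test for REC reporting.

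The cost is two words and at most a few extra SAE forms to the Chief Investigator. REC reporting does not change, and nothing in recruitment, data collection or analysis needs to be altered.
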